7.3.3. AE/SAE Causality—Relatedness Scale

For all collected AEs, the clinician who examines and evaluates the subject will determine the adverse event's causality based on temporal relationship and his/her clinical judgment. The degree of certainty about causality will be graded using the categories below:

- Definitely Related: There is clear evidence to suggest a causal relationship, and other possible contributing factors can be ruled out. The clinical event, including an abnormal laboratory test result, occurs in a plausible time relationship to study product administration and cannot be explained by concurrent disease or other drugs or chemicals. The response to withdrawal of the product (de-challenge) should be clinically plausible. The event must be pharmacologically or phenomenologically definitive, with use of a satisfactory re-challenge procedure if necessary.
- Possibly Related: there is some evidence to suggest a causal relationship (e.g., the event occurred within a reasonable time after administration of the study product). However, the influence of other factors may have contributed to the event (e.g., the subject's clinical condition, other concomitant events). Although an adverse event may rate only as "possibly related" soon after discovery, it can be flagged as requiring more information and later be upgraded to as appropriate.
- Unlikely: a clinical event, including an abnormal laboratory test result, whose temporal relationship to the study product makes a causal relationship improbable (e.g., the event did not occur within a reasonable time after administration of the study product) and in which other drugs or chemicals or underlying diseases provide plausible explanations (e.g., the subject's clinical condition, other concomitant treatments).

- Unrelated/None: the AE is completely independent of study product administration, and/or evidence exists that the event is definitely related to another aetiology. There must be an alternative, definitive aetiology documented by the clinician.
- Expected Events Related to Disease Process: expectedness refers to the awareness of adverse events previously observed, not on the basis of what might be anticipated from the pharmacological properties of the Study Product.

7.3.4. Recording/Documentation

At each contact with the subject, information regarding adverse events will be elicited by appropriate questioning and examinations and will be immediately recorded on a source document. Source documents will include: progress notes, laboratory reports, consult notes, phone call summaries, survey tools and data collection tools. Source documents will be reviewed in a timely manner by the research team. All reportable adverse events that are identified will be recorded on an appropriate case report form (CRF) if applicable. The start date, the stop date, the severity of each reportable event, and the PI's judgment of the AEs relationship to the Study Product/intervention will also be recorded in the Subject's progress notes or on the CRF if applicable.

7.3.5. Specific Serious Adverse Event Requirements

SAEs will be handled according to good clinical practices associated with Serious Adverse Events. SAEs will be recorded in the study's SAE form and clinician progress notes and require expeditious handling and reporting to the Sponsor.

Follow-up information which becomes available as the SAE evolves, as well as supporting documentation, will be collected subsequently and reported to the Sponsor. The PI will report SAE events to the IRB if applicable, in compliance with IRB requirements.

7.3.6. Reporting of Pregnancy

Should a woman become pregnant or suspects she is pregnant while participating in this study, she is instructed to inform study staff and her primary care provider immediately.

7.4. Type and Duration of the Follow-up of Subjects after Adverse Events

7.4.1. Monitoring of Subjects

At each contact with the subject, the investigator must seek information on adverse events by specific questioning and, as appropriate, by examination.

AEs may be observed by the Investigator and/or study staff, elicited from the subject and/or family member, or volunteered by the study subject. Adverse events that had previously been reported by study subject will also be reassessed for duration, intensity and possible reoccurrence. Assessment of safety will include clinical observation and monitoring of haematological, chemical, and immunologic parameters.

Any AE that occurs between the times a study Subject signs the informed consent form and the time s/he departs the study at the end of the final visit (or at the time of early discontinuation of the subject from the study for any reason) will be captured and recorded.

Due to the nature and composition of the study product, no delayed toxicities or withdrawal effects are expected after a subject has discontinued participation in the study. Therefore, no collection of safety information will be done after subject's discontinuation from the study granted that the subject does not have any unresolved AEs.

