- Any sound medical, psychiatric and/or social reason which, in the opinion of the PI, would preclude safe participation in this study or interfere with compliance.
- Abnormal laboratory findings including: abnormal blood counts (haematocrit < 33% or > 47%; WBC < 3.0 or > 12.0 $\times 10^3/\text{mm}^3$; platelets < 140 or > 500 $\times 10^9/\text{L}$); abnormal kidney function test (creatinine > 2.5 mg/dL) or liver function test(s) (AST, ALT, alkaline phosphatase) > 1.5X the upper limit of normal; serum calcium > 11 mg/dL; serum K < 3.5 mEq/L; Na < 134 or > 148 mmolL⁻¹

3.1.8. *Women of Childbearing Potential*

Contraception: the effects of the study products on the developing human fetus have not been studied extensively. For this reason, women of childbearing potential must agree to use adequate contraception (hormonal or barrier method of birth control; abstinence) prior to study entry and for the duration of study participation. Females of childbearing potential will have a pregnancy test prior to receiving study products. Should a woman become pregnant or suspect she is pregnant while participating in this study, she should inform study staff and her primary care physician immediately.

Pregnancy: because there is an unknown but potential risk for adverse events in pregnant women during treatment with the study products, pregnant women are not eligible for study participation.

Breast-feeding: Because there is an unknown but potential risk for adverse events in nursing infants secondary to treatment of the mother with the study products, breastfeeding mothers are not eligible for study participation.

3.2. *Recruitment*

The participants will be identified within the intervention groups of the previous clinical studies (*Studio degli effetti della dieta mima-digiuno e della dieta della longevità sulla composizione corporea, fattori di rischio per malattie età-correlate e marcatori dell'invecchiamento in uno studio randomizzato 1 and 2*) who are willing to start a new study for other 12 months, and who completed the study less than 6 months prior to starting the new study and achieved the study's objectives. Blood tests and a nutritional assessment will be conducted, serving as the baseline for the new study. The recruitment period will last up to 3 years

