7.2. Definition of a serious adverse event (SAE)

A SAE is defined as an AE meeting one of the following outcomes:

- Death during the period of protocol defined surveillance.
- Life Threatening Event (defined as a subject at immediate risk of death at the time of the event).
- Inpatient hospitalization or prolongation of existing hospitalization during the period of protocol defined surveillance.
- A congenital anomaly or birth defect
- A persistent or significant disability/incapacity.
- Any other important medical event that may not result in one of the above outcomes, may be considered a serious adverse event when, based upon appropriate medical judgment, the event may jeopardize the subject and may require medical or surgical intervention to prevent one of the outcomes listed above. Examples of such medical events include allergic bronchospasm requiring intensive treatment in an emergency room or at home, blood dyscrasias or convulsions that do not result in inpatient hospitalization, or the development of drug dependency or drug abuse.

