7.4.2. Follow-up of Subjects after Adverse Events

All SAES and non-serious AEs reported in this study will be followed until resolution or until the investigator and the clinical/medical monitor are in agreement that the AE/SAE has stabilized and no more follow-up is required. This requirement indicates that follow-up may be required for some events after the patient discontinues participation from the study.

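### A birth defect counts as an SAE, but the protocol has no pregnancy-outcome follow-up and does not say whether a pregnancy keeps safety collection open after exit

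*Protocol*

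**What the plan says.** Section 7.2 lists six SAE outcomes, one of which is "A congenital anomaly or birth defect". The entries for death and hospitalization are tied to the protocol's surveillance period; the birth-defect entry has no time limit.

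Section 3.1.8 allows women of childbearing potential to enrol if they agree to contraception. Its stated reason is that "the effects of the study products on the developing human fetus have not been studied extensively".

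Section 7.3.6 covers pregnancy reporting in one sentence. A woman who is or may be pregnant is the only person given a task: "she is instructed to inform study staff and her primary care provider immediately". No step follows for the investigator or the sponsor.

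Section 7.4.1 captures AEs from consent until the end of the final visit or early discontinuation. It says that no delayed toxicity is expected and concludes: "Therefore, no collection of safety information will be done after" the "subject's discontinuation from the study granted that the subject does not have any unresolved AEs". Section 7.4.2 follows AEs and SAEs already reported until they resolve or stabilise, and adds: "This requirement indicates that follow-up may be required for some events after the patient discontinues participation from the study".

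Table 1 schedules pregnancy tests at screening, at baseline and at follow-up visit 2 (T2), the last visit, 12 months after baseline.

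**The concern.** The sections do not fit together. Section 7.2 asks for an outcome that usually becomes visible at birth. Section 7.4.1 closes collection on the ground that nothing delayed is expected, although 3.1.8 says that the fetal question has not been examined extensively. Section 7.3.6 is where a link between the two would be expected, but it stops at notification. The T2 test adds to the difficulty: it can reveal a pregnancy on the day collection closes, and no rule says what is then recorded.

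At stake is how a safety statement can be read. A report of no birth-defect SAEs could mean that none occurred, or only that pregnancy outcomes were not collected. As written, which of the two applies could depend on how each investigator classifies a pregnancy.

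**Working it through.** The protocol gives no figure on this point, so there is none to reproduce. The check has two parts: whether the existing exception reaches a birth after exit, and what share of births would fall after exit.

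**Reach of the exception.**

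1. The exception in 7.4.1 needs an unresolved AE. Section 7.1 defines an AE broadly, as an unanticipated or unintended medical occurrence in a study subject. It neither includes nor excludes pregnancy.
2. If the pregnancy is recorded as an AE and is open at exit, 7.4.1 and 7.4.2 keep follow-up going. The same holds for a complication or a prenatally detected anomaly recorded before exit.
3. If no AE is recorded, nothing is open at exit. A defect first seen at a later birth was never reported during the study, so 7.4.2 has nothing to follow.
4. A newborn is also not plainly a study subject under 7.1, and 7.2 defines an SAE as an AE with a listed outcome. This makes the route to the birth-defect criterion less certain still.

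**Timing.**

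Inputs:
- Follow-up T = 12 months (section 3.3).
- Conception-to-birth interval of w weeks. The documents do not give it; the assumed range is 34 to 40 weeks, with 38 as base case.
- Conceptions spread evenly over the 12 months (assumption).

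With g = w × 7 / 30.4375 months, a birth falls inside the window only if conception occurs before month T − g. The share of births after the final visit is g / T.

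- w = 34: g = 7.82 months; share = 7.82 / 12 = 65%.
- w = 37: g = 8.51; share = 71%.
- w = 38: g = 8.74; share = 73%. Only conceptions in the first 12 − 8.74 = 3.26 months lead to a birth before T2.
- w = 40: g = 9.20; share = 77%.

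The share exceeds one half when g exceeds 6 months, that is, when w exceeds 6 × 30.4375 / 7 = 26.1 weeks. So most births fall outside the window at every value in the assumed range.

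These are shares of follow-up time, not of time on product. Section 3.3 describes five cycles of five days, or 5 × 5 = 25 days of intake.

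**The case against.** The strongest reply is that the protocol already has an escape clause. Read in full, the 7.4.1 sentence exempts subjects with unresolved AEs, and 7.4.2 expects some follow-up after exit. Among women who have agreed to contraception, a pregnancy can fairly be called unintended and recorded as an AE under 7.1. This stands as a possible reading. It does not close the gap, because the protocol does not state it and 7.3.6, the natural place for it, is silent.

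Three stronger readings are tempting, and the documents do not support them.

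- A reader might infer that birth outcomes can never be captured. The exception can reach a pregnancy held open as an AE, and on the timing above about 23% to 35% of births fall inside the window anyway.
- A reader might infer that all births are lost because a pregnant woman leaves the study. No section withdraws her from the study. Section 3.1.8 makes pregnancy a bar to eligibility, and 7.4.5 concerns stopping the study product, whereas the cut-off in 7.4.1 is discontinuation from the study.
- A reader might infer that the protocol calls fetal risk unknown. In the pregnancy paragraph that word is applied to the women: "because there is an unknown but potential risk for adverse events in pregnant women during treatment with the study products". The breast-feeding paragraph uses it for nursing infants. For the fetus, the text says only that effects have not been studied extensively.

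It is also fair to say that few pregnancies are likely, given required contraception and pregnancy testing, and that so few cases could not establish or exclude a risk. That bears on severity, not on whether the sections agree.

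**Conclusion.** The point holds as an unresolved inconsistency in the safety text. Section 7.2 names an outcome that 7.3.6 does not follow up and that 7.4.1 places outside the collection window in most cases, unless the pregnancy is treated as an unresolved AE, which the protocol does not state. Its size is about 65% to 77% of births from in-study conceptions, assuming evenly spread conceptions and 34 to 40 weeks to birth. The number of pregnancies cannot be derived from the documents, which give neither the number of women of childbearing potential nor a pregnancy rate. Women of that age are nevertheless within scope: the parent trial enrolled from age 30, and a 30–50 subgroup is planned.

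Severity is minor. The fat-mass endpoint and its analysis are unaffected.

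**What to change.** Reconcile 7.2, 7.3.6, 7.4.1 and 7.4.2 on data collection only; nothing here concerns care or use of the product.

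- In 7.4.1, extend the exception from unresolved AEs to any pregnancy reported or detected from consent to the final visit. This matches the AE window, and it should expressly include conceptions shortly before the first cycle, which a test could miss. A positive T2 test is then covered.
- In 7.3.6, state that the investigator reports the pregnancy to the sponsor and records its outcome by one contact after the expected delivery date, so that the 7.2 criterion can be applied.
- Add a matching line to the consent form.

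The cost is a few sentences and about one telephone call per pregnancy. The database would close later for those few cases. A conception too recent to be detected at T2 could still be missed, which is a small remaining limit.

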7.4.2. Follow-up of Subjects after Adverse Events

All SAES and non-serious AEs reported in this study will be followed until resolution or until the investigator and the clinical/medical monitor are in agreement that the AE/SAE has stabilized and no more follow-up is required. This requirement indicates that follow-up may be required for some events after the patient discontinues participation from the study.

7.4.3. Modification of Study Product(s)/Intervention(s) for a Subject

No food substitutes are permitted. A reduction of food products, a hold of food or discontinuation of food product is allowed at the discretion of the study clinician.

7.4.4. Halting Rules for the Protocol

The PI will closely monitor and analyze study data as it becomes available and will make determinations regarding the presence and grading of adverse events. Evaluation of adverse events will be analyzed for the study products and with regard to the known complications associated with administration. The study will be halted (no new enrollments and no further administration of product) by the investigators and a report will be submitted to the IRB (if applicable) if a safety issue is identified.

7.4.5. Stopping Rules for an Individual Subject

A study subject will be discontinued from further Study Product(s) administration for:

a significant reduction of BMI greater than 15% from baseline measurement and in any case of a BMI measurement lower than 22 Kg/m² for women and 23 Kg/m² for men during the follow-up visits; any clinical adverse event, laboratory abnormality, concurrent illness, other medical condition.

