1.2. Fasting Mimicking Diet

The fasting-mimicking diet (FMD) is a 5-day meal program to be consumed every 1 to 6 months based on an authorized healthcare professional's recommendation. It is designed to promote the body's natural ability to protect, regenerate and rejuvenate itself. In clinical studies, FMD has been shown to reduce abdominal fat and maintain healthy levels of blood glucose, C-reactive protein (CRP), and insulin-like growth factor 1 (IGF-1) (Wei et al., 2017). Well-designed clinical trials, such as the study conducted by Houston et al. utilizing an independent review board (IRB) approved protocol, have demonstrated the safety and short-term benefits of plant-based nutraceuticals and food restriction in individuals with chronic hypertension (Houston et al., 2014).

A large ongoing randomized, open-label trial aimed at evaluating the effects of two different dietary interventions, FMD and LD, on body composition and cardiovascular (CV) biomarkers in a real word population (NCT05698654) is actually ongoing. This trial started in January 2024 will enrol 501 adult subjects between the ages of 30 and 65: 167 subjects randomized to the FMD arm with a 5-day meal program once every three months for a 6-month period (arm 1); 167 subjects randomized to follow the FMD plus a Longevity Diet program (FMD+LD) for a 6-month period (arm 2); 167 randomized to the control group (arm 3) that will continue their usual diet. On 2024,410, participants were enrolled and randomly assigned to FMD, FMD + LD, or control arm. Although preliminary data demonstrated the beneficial effects of such nutritional plans on body weight, BMI, body composition, and cardiovascular (CV) biomarkers, limited data is available on the long-term effects of these powerful nutritional interventions.

2. Study Objectives/Endpoints

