2.2. Endpoints

- 2.2.1. *Primary endpoint*: maintenance of at least 50% of the fat mass lost during the previous trial and measured after one follow up year on FMD every 3 months
- 2.2.2. *Secondary endpoints*: maintenance of at least 50% of one or more risk factors improvements achieved during the previous clinical trial and measured after one year of follow up FMD cycles every 3 months including improvements in: body mass, body mass index, blood pressure, IGF-1, haemoglobin A1c, fasting glucose, LDL, total cholesterol, and C-Reactive Protein. Determine long-term trends in the reduction/stabilization in the use of antihypertensive and glucose-lowering drugs or other commonly used medications.

3. Study Design

Follow up clinical trial including participants of the approved studies “*Studio degli effetti della dieta mima-digiuno e della dieta della longevità sulla composizione corporea, fattori di rischio per malattie età-correlate e marcatori dell'invecchiamento in uno studio randomizzato*” and “*Studio degli effetti della dieta mima-digiuno e della dieta della longevità sulla composizione corporea, fattori di rischio per malattie età-correlate e marcatori dell'invecchiamento in uno studio randomizzato-2*” that will follow 5-day of the FMD meal program every three months, for one year.

Selection and withdrawal of subjects of the previous clinical study

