3.1.1. Inclusion Criteria

Individuals already included in the aforementioned previous studies *who were assigned to one of the 2 intervention arms: Fasting mimicking diet or fasting mimicking diet plus Longevity diet* and who completed the study less than 6 months prior to starting the new study. Blood tests and a nutritional assessment will be conducted, serving as the baseline for the new study.

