3.1.4. Medical History and Concurrent Diseases

- A history of allergy or intolerance to study products. Detailed descriptions of study product are included in Section 4.1 and 4.2, appended to the Study Informed Consent.
- Clinically significant vital sign abnormalities (systolic blood pressure <90 mmHg or >200 mmHg, diastolic blood pressure <50 mmHg or >105 mmHg or resting heart rate of <50 or >100 bpm) at screening visit.
- A serious, unstable illness including cardiac, hepatic, renal, gastrointestinal, respiratory, endocrinologic, neurologic, immunologic, or hematologic disease.
- Known infection with HIV, TB or Hepatitis B or C.
- A current diagnosis or personal history of:
 - any cardiovascular disease including myocardial infarction, angina, cardiovascular surgery (within 5 years), congestive heart failure, cardiac arrhythmias or conduction abnormalities, cerebrovascular accident, transient ischemic attack (TIA), or peripheral vascular disease, deep vein thrombosis or pulmonary embolus. Diabetes mellitus requiring inhaled or injected insulin.
 - Any significant liver or kidney disease such as cirrhosis or non-alcoholic fatty liver disease, glomerulonephritis, and/or ongoing dialysis treatment.
 - Any malignancy (with the exception of adequately treated malignancies with no known recurrence for >2 years).
- Any serious mental illness including a history of attempted suicide.

- Any medical condition that in the opinion of the primary care doctor or a specialist would preclude safe participation in this study or interfere with compliance.

3.1.5. *Substance Use*

- History of regular intake of >14 alcoholic drinks per week for females, and >21 drinks per week for males (1 drink = 35 cl. beer, 12 cl. wine, or 30 ml. hard liquor).

3.1.6. *Technical reasons*

Any condition in which bioelectrical impedance testing would be impossible or uninterpretable (e.g. prostheses in extremities on both sides, limb amputation, implanted pacemaker, inability to lay still or supine, or skin defects on preferred electrode placement sites).

3.1.7. *Other Exclusion Criteria*

Inability to comply with study and/or follow-up visits.

- Any concurrent condition (including clinically significant abnormalities in medical history, physical examination or laboratory evaluations) which, in the opinion of the PI, would preclude safe participation in this study or interfere with compliance.

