3.3. Scheduled clinical visits

The assessment schedule (Table 1) lists all the assessments and when they are to be performed. Subjects will meet with study staff. When the visit doesn't include blood collection or BIA the visit can be made remotely. During the clinical visits, staff will review calendars, assess for signs and symptoms of adverse events, review compliance to the study product and answer any questions from the subject. Eligible participants will receive 3 different visits (Baseline visit (t0), and two follow-up visits (after 6 and 12 months from the baseline). Eligible participants will be telephonically contacted at the end of each FMD cycle (day 6) in order to assess signs and symptoms of adverse events, compliance to the nutritional intervention (see Appendix A, B), to answer to the questionnaire for dietary recall (see Appendix C).

4. Table 1 reports the timeline of the clinical visits and the activities scheduled. All data obtained from these assessments must be supported in the participant's source documentation.

	Screening Visit	Baseline visit (T ₀)	Follow-up visit 1 (T ₁)	Follow-up visit 2(T ₂)
Informed Consent	✓			
Review Eligibility Criteria	✓			
Start of intervention				
Physical examination ¹		✓	✓	✓
Vital Signs ²	✓	✓	✓	✓
BIA		✓	✓	✓
Peripheral Blood for genetic analysis		✓		✓
Hematological analyses ³		✓		✓
Pregnancy test	✓	✓		✓
AE and SAE collection		✓	✓	✓
Primary and secondary endpoints assessment		✓	✓	✓
Medications	✓	✓		✓

¹ height, weight (dress weight), waist and hip circumferences. ² Body temperature, blood pressure, pulse, respiratory rate. ³ Lipid profile (total cholesterol, LDL-cholesterol, HDL-cholesterol and triglycerides, serum/plasma, albumin, alkaline phosphatase, insulin-like growth factor 1 (IGF-1), Insulin-like growth factor-binding protein 1 (IGFBP1), creatinine, insulin, C-reactive protein (CRP),

aspartate aminotransferase (AST), alanine aminotransferase (ALT), homocysteine, glucose, glycosylated hemoglobin (HbA1c).

Screening and Baseline visit

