Potential participants already subjected to a 5-day fasting-mimicking diet (FMD) program either alone or in combination with the longevity diet previously enrolled in one of the two interventional arms and who completed the clinical study NCT05698654 less than three months before the enrolment period will be contacted *via* telephone to determine preliminary eligibility and interest. Once participants meet all inclusion/exclusion criteria, they will be offered by study staff the opportunity to learn more about the research opportunity before any procedure is performed. Participants meeting eligibility will be then invited to attend a baseline and two follow-up visits

Baseline visit will include measurement of height, weight, and vital signs (body temperature, blood pressure, pulse, respiratory rate), completion of medical history questionnaire, review of medical history and current medications, and collection of fasting blood (12 mL: 6 mL for serum, 6 mL for plasma). Blood testing will include: complete blood count (CBC), glycated hemoglobin (HbA1c), glucose, insulin, lipid profile (total cholesterol, LDL-cholesterol, HDL-cholesterol and triglycerides), AST (GOT), ALT (GTP), alkaline phosphatase, creatinine, reactive C protein (PCR), albumin, insulin, IGF-1, IGFBP1, homocysteine as well as a urine pregnancy test in females of child-bearing potential. Fasting is defined as 12 hours of refraining from consumption of food and beverages though unlimited consumption of water is allowed and encouraged. Participants will be given three boxes of FMD together with ketone test strips to self-monitor urinary ketone bodies during the FMD cycles. Detailed information on the FMD plans will be also given during the visit. Baseline visit will also include body composition assessment using Bioelectrical Impedance Analysis (BIA), measurement of height, weight, and vital signs, medical history, current medications and a collection of fasting blood for the genetic analysis (25 mL: 7.5 mL for serum, 7.5 mL for plasma, 10 mL for white blood cells). Note, the typical draw volume for blood donation in Italy is ~450 mL. Blood testing information will be also retried from the screening visit.

Follow-up visits

The follow-up visits will be carried out after three (follow-up visit 1) and five (follow-up visit 2) FMD cycles (6 and 12 months), in order to evaluate the progress of the trial.

Follow-up visit 1

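### The BMI floor in 7.4.5 applies only at follow-up visits and entry sets no BMI minimum, so someone already below it at T0 can take three of five FMD cycles before a mandatory stop

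*Protocol*

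**What the plan says.** Section 7.4.5 has two BMI triggers for stopping product. One is relative: a fall of more than 15% from baseline. The other is absolute, and is limited to certain visits: "in any case of a BMI measurement lower than 22 Kg/m² for women and 23 Kg/m² for men during the follow-up visits".

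On entry, 3.1.1 admits people from the two intervention arms of the earlier studies who finished less than 6 months before. It adds: "Blood tests and a nutritional assessment will be conducted, serving as the baseline for the new study". Other entry limits are numeric, for example in 3.1.4: "Clinically significant vital sign abnormalities (systolic blood pressure <90 mmHg or >200 mmHg". Section 3.1.7 does the same for blood counts, creatinine, liver enzymes and electrolytes. Nowhere in 3.1.1 to 3.1.8 is there a BMI minimum.

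Table 1 schedules a physical examination at T0, T1 and T2, which its first footnote defines as "height, weight (dress weight), waist and hip circumferences". Of the baseline visit, 3.3 says: "Participants will be given three boxes of FMD together with ketone test strips". The same section places follow-up visit 1 after three cycles (6 months), when the boxes for the last two cycles are given out, and follow-up visit 2 after five cycles (12 months).

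**The concern.** The protocol treats a BMI under 22 or 23 as a reason to stop product once the study is running, but does not apply the same value at the visit where product is first dispensed. The BMI is already available at T0, so the rule acts late on a known value.

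Two things are at stake. The first is avoidable exposure to product that the protocol's own rule will then withdraw. The second is the primary endpoint, which 2.2.1 defines as fat mass "measured after one follow up year on FMD every 3 months". A participant stopped at visit 1 cannot deliver that outcome as planned.

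The entrants make the case conceivable. They come from arms for which section 1.2 says "preliminary data demonstrated the beneficial effects of such nutritional plans on body weight, BMI, body composition", and 3.2 (Recruitment) asks for people who "achieved the study's objectives".

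**Working it through.** **When the floor applies.** Table 1 and 3.3 list the baseline visit (T0) separately from follow-up visits 1 and 2. A rule tied to the follow-up visits therefore first applies at T1. Before T1 the only other scheduled contacts are telephone calls after each cycle, and neither weight nor BMI is listed for them.

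**Cycle count.** Cycles every 3 months over 12 months fall at months 0, 3, 6, 9 and 12, which makes 5, of which 3 fall by month 6. The boxes agree: 3 at T0 + 2 at T1 = 5. This reproduces the protocol's three and five.

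**Exposure before the first check.** At 5 days per cycle (section 5): 3 × 5 = 15 days of 5 × 5 = 25, so 15/25 = 60%.

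**Time off product at the endpoint.** For someone stopped at visit 1 and kept in follow-up: 12 − 6 = 6 months.

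**Does the 15% rule close the gap?** It triggers below 0.85 × T0 BMI. A woman at 21.5 would have to fall below 0.85 × 21.5 = 18.3, and a man at 22.5 below 0.85 × 22.5 = 19.1. Someone already under the floor at T0 is therefore not caught by it, and the change can in any case be assessed only at the next clinic weight, at T1.

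**How plausible is a T0 value below the floor?** The protocol does not give BMI at the start of the earlier trials, so the starting values B below are assumptions. The fall that brings a participant down to the floor by T0 is (B − floor)/B:

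| Assumed starting BMI | Women (floor 22) | Men (floor 23) |
|---|---|---|
| 24 | 2/24 = 8.3% | 1/24 = 4.2% |
| 25 | 3/25 = 12.0% | 2/25 = 8.0% |
| 27 | 5/27 = 18.5% | 4/27 = 14.8% |
| 30 | 8/30 = 26.7% | 7/30 = 23.3% |

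The situation is plausible mainly for people who started near or below 25, more so for men, and remote for those who started at 27 or above.

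**The case against.** The strongest reply is that nobody can be shown to be affected. Only completers of the earlier intervention arms can enter, and those trials may have had their own BMI minimum, which this document does not show. The baseline BMI subgroups in 8.6.4 start at 25, which suggests the planners did not expect lean entrants. From a starting BMI of 25, the loss needed is more than 12% (women) or 8% (men), still present at T0.

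Existing provisions could also catch such a person. The investigator may exclude on medical grounds (3.1.7), the clinician may hold or discontinue food (7.4.3), and 7.4.5 also stops product for other medical conditions. Section 7.4.7 allows replacement. The product is one these participants have already taken, and the protocol does not call 22 or 23 a harm threshold.

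Most of this stands as a limit on size: the number affected is unknown and may be zero, and no stated safety limit is breached. It does not remove the gap. The subgroups are analysis categories, not an entry rule. The discretionary provisions carry no BMI value, whereas the stop at follow-up is mandatory. Replacement comes after the exposure has happened. A BMI minimum in the earlier trials, if there was one, would not by itself say where BMI stands at T0 after an intervention reported to benefit weight and BMI.

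**Conclusion.** The concern holds, as a minor point. As written, the protocol lets a participant who is below 22 (women) or 23 (men) at T0 take 3 of 5 cycles and then requires a stop at visit 1 unless BMI has risen. That path is possible, not automatic, because investigator or clinician discretion may intervene.

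Confidence is high about what the text says and does not extend to how often the case would arise. The six-month gap before the endpoint assumes that the participant stays in follow-up after product stops.

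**What to change.** Add one exclusion to 3.1.2: BMI at the baseline visit (T0), calculated before any FMD box is dispensed, below 22 kg/m² for women or 23 kg/m² for men. It uses the height and weight already scheduled at T0, and 7.4.5 can stay as it is. For a participant below the floor at T0, exposure falls from up to three cycles to none.

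The cost is one line of text and possibly a few fewer eligible participants. Those lost would tend to be leaner and may include strong earlier responders, which changes the population somewhat in a study of maintenance; the size of that change cannot be estimated from the document. They would have to stop product at visit 1 anyway unless their BMI rose. The exclusion does not cover someone just above the floor at T0 who drops below it after the first cycle. That person would still first be checked at visit 1.
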